Puget Sound Psychiatry Center
[name]
[name]

**“A Randomized, Open Label, Sleep Hygiene Controlled 6-Week
Study to Compare the Efficacy of four (CBT-I, FOA, Combined
CBT-I and FOA and Sleep Hygiene) Different Behavioral
Approaches for the Treatment of Adult Subjects with
Insomnia”**

PSPC-17-01
NCT- 03461666

Protocol Date: 02-12-2018
Version 1.2

Confidentiality Statement:

This document is the property of Puget Sound Psychiatry Center (PSPC), Bothell WA and may not—in full or part—be passed on, reproduced, published, distributed, or submitted to any regulatory authority without the express written permission of PSPC.

2.0**SYNOPSIS AND SCHEDULE OF EVALUATIONS**

CLINICAL STUDY SYNOPSIS: Study PSPC-17-01	
Study Number	PSPC-17-01
Title of Study	A Randomized Open Label, Sleep Hygiene Controlled 6-Week Study to Compare the Efficacy of four (CBT-I, FOA, Combined CBT-I and FOA and Sleep Hygiene) different Behavioral Approaches for the Treatment of Adult Subjects with Insomnia.
Study Center (Country)	Puget Sound Psychiatric Center, [name](United States)
Development Phase	Prospective Study
Objective	The current study seeks to evaluate and compare the effectiveness of (1) cognitive behavior therapy for insomnia [CBT-I], (2) focus of attention [FOA], (3) a combination of cognitive behavior therapy for insomnia and focus of attention, and (4) a sleep hygiene control intervention.
Methodology	Allocation: Randomized (1; 1; 1; 1) Intervention Model: Parallel Assignment Primary Purpose: Treatment
Number of Patients	40/group or 160 totals. It is estimated that 320 prospects will need to be screened in order to have 40 per group for a total of 160 participants.

Diagnosis and Main Criteria for Inclusion.	Male and female outpatients who are 18 or older to 72 years. Insomnia Severity Index > or = 10 Meet diagnostic criteria for Insomnia Disorder per DSM-5 Willing and able to sign Informed consent form Not planning on moving away from the area for the subsequent 12 weeks.
Exclusion Criteria	
Participants who answer “yes” to any of the following will be excluded:
 
Females who are lactating or who are pregnant
 
Night shift workers, and individuals who nap 3 or more times per week over the preceding month
 
Consumption of caffeine beverages (i.e. tea, coffee, or cola) comprising usually more than 5 cups or glasses per day
 
Participation in another trial for insomnia
 
Persons unable to complete the study questionnaires and psychological tests
 
Persons who are unable to participate for the entire duration of the study, or in the opinion of the investigators, are likely to be non-compliant with the obligations inherent in the trial participation
 
Persons self-describing with severe anxiety or severe depression (BDI score of 29 or higher) or severe anxiety (BAI score of 36 or higher).
 
Persons with a history of epilepsy, seizures, or dementia
 
Any significant, severe or unstable, acute or chronically progressive medical or surgical condition
 
Serious head injury or stroke within the past year
 
Current alcohol or substance abuse/dependence (must have >90 days of sobriety)
 
Presence of other neurological disorders (e.g., multiple sclerosis, Parkinson's Disease)
 
Presence of an untreated or unstable medical or psychiatric comorbid condition (e.g., major depressive disorder or psychotic disorder requiring admission within the last two years). People using psychotropic medication, hypnotic or sedative medications may be included if they are on a stable dosage for the last 2 months prior to the study, if the dose remains stable throughout the study, and if the medication is judged to not interfere with the study outcomes.
 
Currently on medications known to produce insomnia (e.g., stimulants)
 
Sleep apnea (AHI >15) or previous diagnosis of sleep apnea???
 
Study participants who use a continuous positive airway pressure (CPAP) device for sleep apnea will be eligible for participation if they are below the apnea/hypopnea cutoff while using CPAP and agree to use the device during study participation.

Test Product, Dosage, and Mode of Administration	Behavioral intervention, Six sessions, one hour each. In person.
Duration of Treatment	Treatment involves six consecutive weekly sessions. The study also includes 3 month, 6 month and 12 month follow-up assessment.
Reference Therapy, Dosage, and Mode of Administration	Cognitive Behavior Therapy for Insomnia (CBT-I) Focus of Attention (FOA) Combined CBT-I and FOA Sleep Hygiene Six sessions, one hour each, in person.
Criteria for Evaluation	
Primary Endpoint	The primary end point is completion of 6 treatment sessions and completion of the 3 month, 6 month and 12 month follow-up assessment. Improvement of insomnia outcome is measured by Self Report Sleep Measures (SRSM).
Key Secondary Endpoint	The Secondary end point is improvement outcomes.
Additional Endpoints	Safety Population: will include all randomized subjects who meet eligibility criteria and meet with their treatment provider for session 1. Intent-to-Treat Population: will include all subjects who meet with their treatment provider for session 1 and for whom the treatment provider determines the subject meets diagnostic criteria for 780.52 Insomnia Disorder. Pre-Protocol (PP) Population: will include all subjects who complete the 6 sessions of treatment as well as the 3 month, 6 month and 12 month follow up assessment. It is estimated that 80% of those who complete session 1 will complete session 6. It is estimated that 80% of those who complete session 6 will complete the 3 month, 6 month and 12 month follow up assessments. This will result in 25 participants who will have completed the entire study

Pharmacogenetics Sampling	There are no pharmacogenetics samplings.
Health Outcomes	
Safety Measures	
In general the potential risks for participants are minimal. The treatment approaches involved in related studies have been shown to be a safe procedure and in most of the published studies people who underwent these procedures did not report any harmful effects.
 
It is nonetheless possible participant (s) may experience some discomforts during the treatment. These may include temporary decrease in time asleep and accompanying daytime drowsiness. Some people may become anxious while initially following the treatment procedures, with increased worry about their sleep difficulty. Anxiety and worry about sleep difficulty are in fact common among persons with insomnia. Therefore identifying and addressing these possibilities will be directly addressed during the treatment, and participants will be given guidance about what to expect and how to manage should these discomforts occur.
 
Persons with certain medical illnesses, certain psychiatric illnesses or other sleep disorders may be at increased potential risk of exacerbation of that illness. This is a possibility for participants with epilepsy, bipolar depression, parasomnia, obstructive sleep apnea or other illnesses which have excessive daytime sleepiness as a feature of the parent disorder. The participant may (or may not) be assigned to a treatment which involves sleep restriction. Sleep loss through sleep restriction may
 
 1) lower the threshold for seizures in persons with epilepsy; 2) precipitate mania in bipolar participants; 3) exacerbate parasomnias; 
prevent adequate ventilation in patients with obstructive sleep apnea; and/or aggravate the day time somnolence to the point where it is no longer safe for the participant to drive, operate machinery and/or make judgments that adequately promote their own and/or the safety and well-being of others.
 
The risk is generally higher when these illnesses are untreated. Prospective participants treated for any of these illnesses and interested in participating must have the written approval of their treatment provider in order to be eligible. Prospective participants will be screened and informed of these potential risks. If any of these risks (1-5 above) occur during the study, the participant will be asked to immediately discontinue the sleep restriction, and an alternative treatment not involving sleep

	restriction will be offered. The participant will also have the option of discontinuing the treatment if they prefer this to proceeding with the alternative treatment which does not involve sleep restriction.
Pharmacokinetic Sampling	There are no pharmacokinetic samplings.
Statistical Analysis	Repeated measures analysis of variance (ANOVA) will be used to test Hypotheses 1, 2 and 3. Chi square will be used to test Hypothesis 4.

SCHEDULE OF EVALUATIONS: Study PSPC-17-01

	Screening	Randomized, Open label, sleep Hygiene Controlled 6 Week study							EOT/ ET (1 week F/U)	Safety Follow up Period		
		1	(BV)/ 2	3	4	5	6	7		8	9	10
Visit #	1	up to 14 days	(BV)/ 2	3	4	5	6	7	8	9	10	11
Study Day Weeks/Months		1W	2W	3W	4W	5W	6W	7W	7W	3M	6M	12M
Informed consent	x											
Review of Histories	x											
Medication History +Concomitant Medications	x											
Inclusion/ Exclusion	x	x	x	x	x	x	x	x	x	x	x	x
Randomization												
Assessment		x										
Questionnaire & Inventories GMS/GMS-I												
ISI	x							x	x	x		x
BDI	x							x	x	x	x	x
BAI	x							x	x	x	x	x
SRSM	x	x	x	x	x	x	x	x	x	x	x	x
WSL								x	x	x	x	x
CGI-I	x	x	x	x	x	x	x	x	x	x	x	x
CGI-S	x	x	x	x	x	x	x	x	x	x	x	x
Q-LES	x							x				
DSM-5 diagnostic Interview	x											
C-SSRS	x	x	x	x	x	x	x	x	x	x	x	x

(GMS) Goal Motivation Scale; (GMS-I) Goal Motivation Scale-Insomnia, Beck Depression Inventory (BDI); Beck Anxiety Inventory (BAI); Insomnia Severity Index (ISI); Self Report Sleep Measures (SRSM); Weekly Sleep Log (WSL);

Clinical Global Impression - Improvement (CGI-I), Clinical Global Impression – Severity scale (CGI-S)

Quality of Life Enjoyment and Satisfaction (Q-LES), End of Treatment (EOT)/Early Termination (One week F/U): (ET)

Columbia suicide severity rating scale (C-SSRS); Baseline Visit (BV)

3.0

TABLE OF CONTENTS

1.0 TITLE PAGE -----	1
2.0 SYNOPSIS AND SCHEDULE OF EVALUATIONS-----	2
3.0 TABLE OF CONTENTS-----	8
4.0 LIST OF ABBREVIATIONS-----	12
5.0 ETHICAL CONSIDERATIONS-----	13
5.1 INSTITUTIONAL REVIEW BOARD AND INDEPENDENT ETHICS-----	13
5.2 COMMITTEE ETHICAL CONDUCT OF THE STUDY -----	13
5.3 PATIENT INFORMATION AND INFORMED CONSENT -----	13
6 INVESTIGATORS AND STUDY ADMINISTRATIVE STRUCTURE-----	14
7 INTRODUCTION-----	15
8 STUDY OBJECTIVES-----	22
9 INVESTIGATIONAL PLAN-----	28
9.1 OVERALL STUDY DESIGN AND PLAN: DESCRIPTION-----	28
9.1.1 IN PERSON SCREENING AND DATA GATHERING-----	28
9.1.2 DSM-5 DIAGNOSTIC SCREENING INTERVIEW-----	28
9.1.3 SAFETY FOLLOW UP PERIOD-----	31

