According to Mitchell et al “There are two main disadvantages to CBT-I. First, during the first few weeks of treatment there is often an acute reduction in total sleep time that can lead to the side effect of increased daytime sleepiness which, for some, is enough to lead them to drop out of treatment. Second, improvements from CBT-I are typically not seen until 3-4 weeks into treatment” (p. 3 of 18). Also noteworthy is the emotional response of patients upon learning their sleep will be restricted, commonly with a markedly later bedtime during the implementation of sleep restriction. Although apparently no research to date has assessed patient satisfaction and/or distress during treatment implementation, this may be a factor related to dropout rate with CBT-I. Among ten randomized controlled trials of CBT-I for primary insomnia reporting dropout rate and involving sleep restriction, dropout rates ranged from 0% to 33%. Specifically, 4 studies reported 0% dropout; 1 study reported 7% dropout; 2 studies reported 8% dropout; and dropout rates of 11%, 18% and 33% were each reported in one study (Table 1, Okajima, Komada & Inoue, 2011). In addition, while 36% remission of insomnia disorder is better than 16.9% (comparison group), this means 64% of those completing CBT-I continued to meet diagnostic criteria for Insomnia Disorder (Wu, Appleman, Salazar and Ong, 2015). With all due respect for the major contribution of CBT-I in assisting those with insomnia, there is room for improvement as evidenced by 64% still having Insomnia Disorder upon completion of treatment.

Another potential limitation of CBT-I relates to the mechanism of change and may lead to a means to improve upon the efficacy of behavioral treatment(s) for insomnia. “Research by [name]. and colleagues has established that insomniacs have faster brain wave patterns in bed than good sleepers which is consonant with heightened mental activity.” (Jacobs, 2000, p. 22). The faster brain wave pattern is only partially addressed in CBT-I which focuses on negative sleep talk. However, the emphasis in CBT-I is upon reality testing and/or challenging negative sleep talk, not upon slowing the faster brain wave pattern itself. A behavioral treatment approach which targets the actual here-and-now brain wave frequency

with the goal of slowing the brain wave frequency in the moment at the time when the person wants to go to sleep may further improve their ability to do so.

BRAIN WAVE FREQUENCY AND SLEEP:

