Walsh JK & Schweitzer PK. Ten-year trends in the pharmacologic treatment of insomnia. *Sleep*. 1999; 22:371-375.

8.0

STUDY OBJECTIVES

The objectives of this study seeks to evaluate and compare the effectiveness of (1) cognitive behavior therapy for insomnia [CBT-I], (2) focus of attention [FOA], (3) a combination of cognitive behavior therapy for insomnia and focus of attention, and (4) a sleep hygiene control intervention.

PRIMARY OBJECTIVE The primary objective is completion of 6 treatment sessions and completion of the 3 months, 6 months and 12 months follow-up assessment. Improvement of insomnia outcome is measured by Self Report Sleep Measures (SRSM).

SECONDARY OBJECTIVE The Secondary objective is improvement outcomes.

SAFETY AND TOLERABILITY END POINTS

In general the potential risks for participants are minimal. The treatment approaches involved in related studies have been shown to be a safe procedure and in most of the published studies people who underwent these procedures did not report any harmful effects. It is nonetheless possible participant(s) may experience some discomforts during the treatment. These may include temporary decrease in time asleep and accompanying daytime drowsiness. Some people may become anxious while initially following the treatment procedures, with increased worry about their sleep difficulty. Anxiety and worry about sleep difficulty are in fact common among persons with insomnia. Therefore identifying and addressing these possibilities will be directly addressed during the treatment, and participants will be given guidance about what to expect and how to manage should these discomforts occur. Persons with certain medical illnesses, certain psychiatric illnesses or other sleep disorders may be at increased potential risk of exacerbation of that illness. This is a possibility for participants with epilepsy, bipolar depression, parasomnias, obstructive sleep apnea or other illnesses which have excessive daytime sleepiness as a feature of the parent disorder. The participant may (or may not) be assigned to a treatment which involves sleep restriction. Sleep loss through sleep restriction may

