9.7.2 ANALYSIS POPULATIONS

1. **Safety Population:** will include all randomized subjects who meet eligibility criteria and meet with their treatment provider for session 1.

2. **Intent-to-Treat Population:** will include all subjects who meet with their treatment provider for session 1 and for whom the treatment provider determines the subject meets diagnostic criteria for 780.52 Insomnia Disorder.
3. **Pre-Protocol (PP) Population:** will include all subjects who complete the 6 sessions of treatment as well as the 3 month, 6 month and 12 month follow up assessment. It is estimated that 80% of those who complete session 1 will complete session 6. It is estimated that 80% of those who complete session 6 will complete the 3 month, 6 month and 12 month follow up assessments. This will result in 25 participants who will have completed the entire study.

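### The declared primary endpoint is completion of sessions and follow-up, which no hypothesis tests, and no single efficacy score is designated primary in its place

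*Protocol*

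**What the plan says.** The Objective row of the synopsis (Section 2.0) gives the purpose: "The current study seeks to evaluate and compare the effectiveness of" CBT-I, focus of attention, their combination and sleep hygiene.

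The Primary Endpoint row then says: "The primary end point is completion of 6 treatment sessions and completion of the 3 month, 6 month and 12 month follow-up assessment". Section 8.0 carries this over: "The primary objective is completion of 6 treatment sessions", again with the three follow-up assessments. In both places the following sentence is "Improvement of insomnia outcome is measured by Self Report Sleep Measures (SRSM", closing the bracket. It gives no item, score, visit or contrast.

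The Key Secondary Endpoint row reads in full: "The Secondary end point is improvement outcomes". Section 8.0 has a matching secondary objective.

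The Statistical Analysis row of the synopsis says: "Repeated measures analysis of variance (ANOVA) will be used to test Hypotheses 1, 2 and 3", and assigns chi-square to Hypothesis 4. The Statistics paragraph of Section 8.0 is wider. It covers Hypotheses 1 to 16, with chi-square for 4 and 11, but ranks none of them.

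**The concern.** A primary endpoint should answer the trial's question. Here the question is which treatment improves insomnia, and the declared endpoint is attendance. An arm could keep every participant without improving anyone's sleep.

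The SRSM sentence does not repair this. It sits in the primary row, but the next row places improvement in the secondary tier, and the SRSM has no single score that could serve. The endpoint row, the secondary row and the analysis row of one synopsis point to different outcomes. Two things are at stake: a primary result that cannot support an efficacy conclusion, and freedom to pick the headline efficacy result after the data are seen.

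**Working it through.** **Does any hypothesis test completion?** The outcomes in Section 8.0 are:

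- Weekly Sleep Log: 1, 8
- ActiWatch: 2, 9
- Insomnia Severity Index: 3, 10
- DSM-5 diagnosis: 4, 11
- SRSM satisfaction, five items: 5, 12, 14
- SRSM distress, one item: 6, 13
- SRSM impairment, three items: 7
- Satisfaction with treatment: 15
- Likelihood to recommend: 16

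Completion: 0 of 16. SRSM: 6 of 16, over three different scores, none called primary. SRSM within the synopsis analysis row (Hypotheses 1 to 4): none.

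**Planned completion.** Section 9.7.2 expects 80% of those completing session 1 to reach session 6, and 80% of those to complete follow-up. 40 × 0.80 × 0.80 = 25.6. The protocol's figure of 25, given without a unit, is therefore per group. The trial total would be 160 × 0.64 = 102.4.

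**Precision of a completion comparison.** The approximate 95% half-width for the difference between two arms of 40 with a common rate p is 1.96 × √(2p(1 − p)/40).

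- p = 0.64: 1.96 × √(2 × 0.64 × 0.36/40) = 0.210, or ±21 points.

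The Missing Data paragraph of Section 8.0 expects only 5 to 10% not to complete the 12 month follow-up, which conflicts with the 20% above. If that loss applies after 80% session completion:

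- p = 0.80 × 0.90 = 0.72: 0.197
- p = 0.80 × 0.95 = 0.76: 0.187

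This is ±19 to 20 points. If it is the only loss:

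- p = 0.90: 0.131
- p = 0.95: 0.096

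This is ±10 to 13 points.

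**Choosing the efficacy result afterwards.** The protocol states no significance level, so 5% per overall four-arm test is assumed, with no true effect on any outcome.

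- Three SRSM change scores (Hypotheses 5, 6, 7): 1 − 0.95³ = 0.143 if independent, and less if positively correlated.
- Hypotheses 1 to 13, the distinct efficacy hypotheses (14 repeats 12 in substance; 15 and 16 concern opinion of the treatment): 1 − 0.95¹³ = 0.487 if independent.
- The same 13 with equal correlation between outcomes: 0.42, 0.35 and 0.25 at correlation 0.3, 0.5 and 0.7. These come from 20,000 simulated trials with 40 per arm and one-way F tests on change; Hypotheses 4 and 11 were treated as F tests for simplicity.

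**Which visits could supply a primary change score?** The SRSM is collected at every visit, so the choice matters.

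- Baseline: Section 9.5.3.2 places randomization after all Visit 2 assessments. The scheduling text under Sections 9.1.2 and 9.4.2 has the provider told the treatment a week ahead, and Section 9.4.6 puts the first session at Visit 2. Visit 1 precedes allocation on either account.
- Post-treatment: Section 9.5.3.8 labels Visit 8 a one week follow-up. Sections 9.1.3 and 9.4.5 allow the end-of-treatment measures from the day of the last session up to one week later.

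**The case against.** The best defence is that the SRSM sentence is the real primary endpoint, that the Statistics paragraph of Section 8.0 does test SRSM scores, and that scoring detail belongs in an SAP not shown here. An SAP can indeed add scoring detail. But the protocol has already stated what is primary, twice, and has put improvement in the secondary tier. An SAP that follows it inherits a retention rate; one that names an efficacy primary contradicts it.

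Completion also has real interest. On patients' reaction to sleep restriction, the introduction says "this may be a factor related to dropout rate with CBT-I". That supports reporting completion as acceptability, not using it as evidence of effect on insomnia.

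Several stronger readings are tempting but not supported:

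- A reader might take 49% as the error rate in play. It is an independence ceiling over correlated sleep outcomes, and the endpoint cell names only the SRSM. Hypotheses 12 and 13 also compare 12 months with post-treatment, which is durability rather than improvement from baseline. The three-score figure fits the cell better, although the analysis row keeps Hypotheses 1 to 4 in view.
- The per-protocol population "will include all subjects who complete the 6 sessions of treatment" and all follow-up assessments, so one might infer that the endpoint is 100% by construction. That is true only within that population. The protocol does not assign the endpoint to it, and an intent-to-treat population is defined.
- One might add that the ANOVA-then-t-test rule inflates error. The protocol states no level and does not say the t-tests are unadjusted. Its hypotheses gate item-level tests on a composite, while its Statistics paragraph can be read differently. The correction can be left to the SAP.
- One might infer that Visit 2 ratings are biased by known allocation. The text says the provider is told in advance. It does not say the participant is, and the first session is the same in all arms. The order needs reconciling; bias is not shown.

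**Conclusion.** The point holds. The primary endpoint and objective as written measure retention in a trial meant to compare effectiveness, no hypothesis tests them, and no efficacy score is designated in their place. This rests on the wording alone and needs no statistical assumption.

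The figures show scale only. Freedom to choose among the three SRSM change scores costs up to 14%. Across all 13 efficacy hypotheses the figure is about 25 to 42% at correlation 0.7 to 0.3, with 49% as the ceiling. All assume 5% per test. The ±21 points for completion assumes 64% in both arms; under the conflicting loss figure in the Missing Data paragraph it is ±10 to 20 points, depending on how that figure is read.

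**What to change.** Before any comparison by arm, amend the Primary Endpoint, Key Secondary Endpoint and Statistical Analysis rows of the synopsis, and the objectives in Section 8.0, as follows:

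- Name one primary efficacy score, its pre- and post-treatment visits, and the overall four-arm contrast of change. The five-item satisfaction composite of Hypothesis 5 fits the text best, because both primary statements name the SRSM. The sponsor may choose another measure.
- Take the baseline from an assessment made before allocation is known. Visit 1 qualifies. Visit 2 qualifies only once Section 9.5.3.2 is reconciled with the scheduling text under Sections 9.1.2 and 9.4.2 and with Section 9.4.6.
- Reconcile the Visit 8 timing in Section 9.5.3.8 with Sections 9.1.3 and 9.4.5, and state one window.
- Report completion by arm with confidence intervals as an acceptability outcome, and reconcile the two expected loss figures.
- Label all other hypotheses secondary or exploratory.

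The cost is a protocol amendment with IRB approval and a signed page under Section 9.9. No new data are needed.
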